### 7.3.3 Safety analyses

Key measures of safety will include:

- the incidence and intensity (according to CTCAE criteria version 3.0) of adverse events
- time course and distribution of patients by maximum CTCAE grade; and
- time course of laboratory changes

The type, number and intensity of adverse events will indicate how well BI 6727 is tolerated. Haematological toxicity such as thrombocytopenia, neutropenia and leukopenia as well as non-haematological toxicity will be evaluated continuously by using the CTCAE scheme.

Specific AE expected to be associated with BI 6727 may be described more accurately.

Frequency distributions and other descriptive statistical measures will be used to examine these variables. The time course of the changes and the reversibility will be displayed.

Descriptive statistics for ECG, in addition to abnormalities and other notable findings will also be analysed.

All data will be presented in the following segments:

- 1. First course of BI 6727
- 2. Data collected overall courses of BI 6727

### 7.3.4 Interim analyses

A pharmacokinetic interim analysis will be performed as soon as pharmacokinetic data of a sufficient number of patients are available and clean. A repeat pharmacokinetic interim analysis will be performed if requested. In contrast to the final pharmacokinetic calculations, the interim analysis will be based on planned sampling times rather than on actual times. Therefore, minor deviations of interim and final results may occur. The interim analysis will provide mean concentration-time profiles and summary statistics of pharmacokinetic

parameters/individual values without trial subject identification. The interim results will be distributed to the Investigator/trial team

#### 7.4 HANDLING OF MISSING DATA

Every effort will be made to obtain complete information on all adverse events, with particular emphasis on potential dose limiting toxicities.

If not stated otherwise, missing data will not be imputed and remain missing. Potential outliers will be reported and analysed as observed.

Tumour evaluation : see RECIST criteria (see ISF, R01-0754) and Appendix 10.4.5 "Handling of missing tumour lesion measurement".

Time to progression:

Patients for whom no tumour assessments are available within the six weeks prior to discontinuation from treatment will be examined on a case by case basis. In case of early stop not related to the disease, patients will be censored at time of EOT.

Pharmacokinetic evaluation: For details refer to Appendix 10.1.

#### 7.5 RANDOMISATION

In this open label, phase I, dose-escalating study, randomisation is not applicable.

Patients will be assigned, not randomized, into escalating dosage groups by order of admission into the trial. Differences in patient characteristics among dosage tiers will be examined carefully for any possible effects on the assessment of the maximum tolerated dose or tumour response.

#### 7.6 DETERMINATION OF SAMPLE SIZE

In oncology trials six patients at the MTD are regarded sufficient to determine DLT. TABLE 7.6: 1 exhibits the probabilities of two or more out of six patients to be observed with DLT for some assumed underlying rates of DLT in the population of all patients. With the escalation scheme in this trial, there will be a probability of at least 80 % for two or more patients to exhibit DLT, if the underlying individual probability for a patient to reach DLT is 42 % or larger.

TABLE 7.6: 1 Assumed population rates of dose limiting toxicity

Individual probability of observing DLT	0.40	0.42	0.45
Probability of observing DLT in two or more out of six patients	0.77	0.80	0.84

Source: Probabilities calculated from the cumulative distribution function of the binomial distribution with n=6 and varying p's

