### **3. DESCRIPTION OF DESIGN AND TRIAL POPULATION**

#### **3.1 OVERALL TRIAL DESIGN AND PLAN - DESCRIPTION**

Due to the methodology of this trial (dose escalation), it is not possible to predict the number of patients necessary to reach the objectives. An estimated total of up to 80 patients might be necessary to establish MTD. A total of 24 patients will be treated at MTD. Actual accrual will depend on the number of dose levels tested and the adverse events observed. Patients non evaluable with respect to MTD will be replaced. Patients with a histologically or cytologically confirmed diagnosis of a malignant solid tumour refractory or not amenable to standard therapies are eligible for this trial. It is planned to have the trial performed at one centre, depending on enrolment more centres may be initiated.

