#### **4.1.6 Selection and timing of doses for each subject**

BI 6727 will be administered as a short infusion over 60 minutes using an infusion pump, on day 1 of each course (the start and end time of the infusion needs to be documented in the e-CRF). Immediately following the infusion of BI 6727 the infusion tubing will be washed with 100 mL physiological sodium chloride (0.9% NaCl) solution for a maximum duration of 10 minutes (The end time of the washing step needs to be documented in the e-CRF). BI 6727 should be administered strictly intravenously.

Initially, three patients will be treated per dose level. When at the ongoing dose level one patient experiences drug-related dose limiting toxicity (DLT; for definition, please refer to section 5.2.1) the number of patients treated at that dose level will be increased to a maximum of six evaluable patients. When no further patient experiences DLT the dose will be escalated to the next level. When two or more patients experience DLT in any dose cohort, other than the

expansion cohort at MTD level, enrolment into this dose cohort will be stopped. In order to define the maximum tolerated dose (MTD) three additional patients will be treated at one dose tier below unless six have already been treated at that dose tier. The MTD (see also section 5.2.1) is the highest dose at which not more than one patient out of six experiences DLT (R01-0028). Should safety data of patients treated at the next lower dose indicate a sufficient safety margin another escalation to an intermediate dose can be chosen after discussion between the investigator and the clinical monitor.

Once the MTD is determined patient enrolment at higher dose tiers will be suspended. Further patients will be included at the MTD level until a total of 24 patients will have been treated at the MTD.

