## 5.2 SAFETY

### 5.2.1. Maximum tolerated dose (MTD) and dose limiting toxicity (DLT)

The maximum tolerated dose is defined as:

The dose of BI 6727 which is one dose tier below that dose at which two or more out of a maximum of six patients experienced DLT. At the maximum tolerated dose, no more than one patient out of six patients may experience DLT, i.e. MTD is defined as the highest dose studied for which the incidence of dose-limiting toxicity is no more than 17% (i.e. 1/6 patients) during the first course.

For definition of DLT, it is essential that patients are treated sufficiently according to supportive care standards. Patients with treatable adverse events that are not sufficiently treated need to be replaced.

Dose limiting toxicity is defined as:

- drug related CTCAE grade 3 or 4 non haematological toxicity (except emesis or diarrhoea responding to supportive treatment), or
- drug related CTCAE grade 4 neutropenia for seven or more days and / or complicated by infection, or
- CTCAE Grade 4 thrombocytopenia .

The MTD will be defined on the basis of DLT observed during the first course of dose escalation cohorts. However, for those patients who receive a further infusion, unusual or unexpected toxicities will be considered for the purposes of confirming the MTD.

Patients with a clinical benefit after a course of BI 6727 (symptom improvement, clinical response or absence of progression) and who recovered from drug related adverse events are eligible for a further treatment course. In case of symptom improvement despite disease progression a repeated course may be allowed in agreement between the clinical monitor and the investigator. All DLT's occurring during the first or repeated treatment courses will be reported as significant adverse events.

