## 6. INVESTIGATIONAL PLAN

This is an open label, uncontrolled trial in patients with various solid tumours following the 3+3 design with dose escalation (R04-0569). The aim is to assess the MTD of BI 6727 administered at escalating doses.

Patients meeting the inclusion and exclusion criteria and who have given their written informed consent are eligible for participation in the trial.

Three to six patients each will be administered BI 6727 at a certain dose level. For exact dosing details refer to section 4.1.3.1. A total of 24 patients will be treated at the MTD.

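### Protocol 7.6 credits the 3+3 escalation scheme with an 80% probability that holds only if six patients are treated at the dose

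*Protocol*

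**What the plan says.** Section 7.6 of the protocol gives the probability of at least two DLTs among six patients as 0.77, 0.80 and 0.84 for individual DLT rates of 0.40, 0.42 and 0.45. For individual rates of 42% and above, the text carries the middle value over to the design as the chance of at least two patients with DLT: "With the escalation scheme in this trial, there will be a probability of at least 80 % for two or more patients". The note to Table 7.6: 1 gives the basis: "Probabilities calculated from the cumulative distribution function of the binomial distribution with n=6 and varying p's".

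The scheme itself is set out in 4.1.6:

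- "Initially, three patients will be treated per dose level".
- After one DLT, "the number of patients treated at that dose level will be increased to a maximum of six evaluable patients".
- When a dose is stopped for two or more DLTs, "three additional patients will be treated at one dose tier below unless six have already been treated at that dose tier".

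Section 6 describes the trial as "following the 3+3 design with dose escalation". Section 5.2.1 places the MTD "one dose tier below that dose at which two or more out of a maximum of six patients experienced DLT".

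**The concern.** The sentence and the table note rest on different designs. The note assumes that six patients are always treated at the dose. The scheme does not guarantee this: a tier with no DLT in its first three patients is passed. The fill-up clause in 4.1.6 makes sense only if tiers can be left with three patients, and 5.2.1 speaks of six as a maximum.

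This is the only operating characteristic the protocol states for its MTD search. A reader may take it as the chance that the scheme halts at a dose with a 42% DLT rate before moving to a higher one. If so, it overstates that chance.

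**Working it through.** **Inputs.** DLT rates p = 0.40, 0.42 and 0.45 (Table 7.6: 1). Three patients first, expansion to six after one DLT, stop at two or more, fill-up of the tier below (4.1.6). Escalation after 0 of 3 (3+3 design, section 6).

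**1. The protocol's figure.** With six patients fixed, P(≥2 of 6) = 1 − (1−p)^6 − 6p(1−p)^5. At p = 0.42 this is 1 − 0.0381 − 0.1654 = 0.7965. At 0.40 and 0.45 it is 0.7667 and 0.8364. All three match the table. The gap between 0.7965 and 0.80 is rounding; exactly 80% is reached at p = 0.4224.

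**2. Before the next tier opens.** Two or more DLTs arise either in the first three patients, or as one in the first three and at least one in the next three:

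f(p) = P(≥2 of 3) + P(1 of 3) × P(≥1 of next 3)

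At p = 0.42:

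- P(0 of 3) = 0.58³ = 0.1951
- P(1 of 3) = 3 × 0.42 × 0.58² = 0.4239
- P(≥2 of 3) = 1 − 0.1951 − 0.4239 = 0.3810
- P(≥1 of next 3) = 1 − 0.1951 = 0.8049
- f = 0.3810 + 0.4239 × 0.8049 = 0.3810 + 0.3412 = 0.722

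f(p) reaches 0.80 at p = 0.476.

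**3. Adding the fill-up.** A tier passed with 0 of 3 can still show two DLTs in a second group of three, but only if the tier above is found too toxic, whether at first pass or after its own fill-up. Working from the top tier down:

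F(tier) = f(p) + P(0 of 3) × P(≥2 of 3) × F(tier above)

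At p = 0.42 the multiplier is 0.1951 × 0.3810 = 0.0743.

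- *Upper limit.* If the tier is always filled after being passed, F = 0.7222 + 0.0743 = 0.7965. This is the fixed-six value, so the table gives the ceiling for the scheme.
- *Equal rates on all higher tiers, long ladder.* F = f / (1 − 0.0743) = 0.7222 / 0.9257 = 0.780. With only one tier above, F is 0.776; with two it is 0.780.
- *Higher tiers at 0.50, 0.60 or 0.70.* F = 0.788, 0.793 or 0.796.

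| DLT rate | Six treated | Before next tier opens | With fill-ups, long ladder |
|---|---|---|---|
| 0.40 | 0.767 | 0.691 | 0.748 to 0.767 |
| 0.42 | 0.797 | 0.722 | 0.780 to 0.797 |
| 0.45 | 0.836 | 0.766 | 0.824 to 0.836 |
| Rate giving 80% | 0.422 | 0.476 | 0.422 to 0.433 |

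A simulation of the rule (12 tiers, 3.2 million paths per case) agrees. At p = 0.42 it gives 0.722 before the next tier opens. With fill-ups it gives 0.780 for equal rates, 0.793 for higher tiers at 0.60 and 0.796 at 0.70.

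**The case against.** The strongest reply is that 72% answers a different question. Section 7.6 does not say that the two DLTs occur before the next tier opens. The fill-up clause also means that a dose below a stopped tier is declared the MTD on six patients, not on 0 of 3. On that reading the right comparison is the whole scheme, where the shortfall at 42% is 0 to 2 points. The 2-point end needs DLT rates that stay flat above 42%, which is unfavourable for an escalation design; once the higher tiers are at about 66% or more, the whole-scheme value itself rounds to 0.80. In addition, the surrounding text, the row label and the source note all refer to six patients, so the basis is not hidden.

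Much of this stands. The table is correct, the whole-scheme gap is small, and a clause added to the sentence would remove the error. It does not rescue the sentence as written. That sentence names the escalation scheme, under which six patients at a dose are not assured, and it does not say that later fill-ups are being counted. Its reader cannot tell whether 80% describes the decision to escalate, where the figure is 72%, or the completed scheme, where 80% is the ceiling.

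**Conclusion.** The point holds and is minor. Table 7.6: 1 is right for six treated patients; the sentence that assigns its value to the escalation scheme is wrong. At a 42% DLT rate the stated 80% is 7 to 8 points too high as the chance of stopping before escalation, and 0 to 2 points too high for the whole scheme.

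The whole-scheme range assumes several tiers above the dose, with DLT rates there no lower than at the dose itself. The documents do not give those rates. The optional intermediate dose in 4.1.6 is not modelled. DLTs in the expansion to 24 patients at the MTD are not counted, because 4.1.6 exempts that cohort from the stopping rule and the table concerns six patients.

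Conduct is unaffected. Escalation follows observed DLT counts, and section 3.1 says of the total that "it is not possible to predict the number of patients necessary to reach the objectives". Section 7.2 plans no formal inference, and SAP 7.7 foresees no statistical model for the MTD.

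**What to change.** Keep the values in Table 7.6: 1, label the row as applying if six patients are treated (binomial, n=6), and replace the sentence with:

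> If six patients are treated, the probability of two or more DLTs is about 80% at a DLT rate of 42%. Under the 3+3 scheme the probability of stopping at such a dose before escalating is about 72%, reaching 80% at a rate of about 48%; counting the later fill-up it is about 78% to 80%, depending on DLT rates at higher tiers.

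The least that would cure the error is to make the existing sentence conditional on six patients being treated at the dose. Optionally, add a second table row for the 3+3 rule before the next tier opens (0.69, 0.72, 0.77), with its own source note giving P(≥2 of 3) + P(1 of 3) × P(≥1 of next 3).

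The cost is one sentence and one row label. Doses, escalation rules and enrolment do not change.

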## 8. ADMINISTRATIVE MATTERS

The trial will be carried out in compliance with the protocol, the principles laid down in the Declaration of Helsinki, version as of October 1996, in accordance with the ICH Harmonised Tripartite Guideline for Good Clinical Practice (GCP)

### Insurance Cover:

The Sponsor (Boehringer Ingelheim) will take out no-fault insurance cover for all subjects included in the study. The conditions of this insurance cover are available to the Investigator and the subjects in the ISF (Investigator Site File)

## 8.1 ETHICS

### 8.1.1 Institutional Review Board or Independent Ethics Committee

The trial will not be initiated before the protocol and informed consent and subject information form have been reviewed and received approval / favourable opinion from the Independent Ethics Committee (IEC) and implicit approval by the Competent Authority. Should a CTP Amendment be made that needs IEC approval and authority notification, the changes in the CTP will not be instituted until the Amendment and revised informed consent (if appropriate) have been reviewed and received approval / favourable opinion from the local IEC. A CTP Amendment intended to eliminate an apparent immediate hazard to subjects may be implemented immediately providing that the appropriate regulatory authorities and IEC are notified as soon as possible and an approval is requested. CTP Amendments only for logistical or administrative changes may be implemented with notification to the IEC only.

The constitution of the IEC must meet the requirements of the participating country / countries. A list of the IEC members, with names and qualifications, needs to be provided. The Sponsor must provide the name and address of the IEC along with a statement from the IEC that it is organised according to GCP and the applicable laws and regulations. The IEC must also perform all duties outlined by the requirements of the participating country / countries. For trials performed under an US IND: The US IND requirements outlined in the US Code of Federal Regulations must also be met.

### 8.1.2 Informed Consent and Patient Information

Prior to subject participation in the trial, written informed consent must be obtained from each subject (or the subject's legally accepted representative) according to the regulatory and legal requirements of the participating country / countries. Each signature must be dated by each signatory and the informed consent and any additional subject information form retained by the Investigator as part of the study records. A signed copy of the informed consent and any additional subject information must be given to each subject or the subject's legally accepted representative.

The subject must be informed that his/her personal trial related data will be used by Boehringer Ingelheim in accordance with the local data protection law. The level of disclosure must also be explained to the subject.

The subject must be informed that his / her medical records may be examined by authorised monitors (CML/CRA) or Clinical Quality Assurance auditors appointed by Boehringer Ingelheim, by appropriate IEC members, and by inspectors from regulatory authorities.

Should a CTP Amendment become necessary, the subject consent form and subject information form may need to be revised to reflect the changes to the CTP. It is the responsibility of the Sponsor to ensure that an amended consent form is reviewed and received approval / favourable opinion from the IEC, and that it is signed by all subjects subsequently entered in the trial and those currently in the trial, if affected by the Amendment.

## **8.2 RECORDS**

### **8.2.1 Drug accountability**

Drug supplies, which will be provided by the Sponsor (or a CRO appointed by the Sponsor), must be kept in a secure, limited access storage area under the storage conditions defined by the Sponsor. Where necessary, a temperature log must be maintained to make certain that the drug supplies are stored at the correct temperature.

The Investigator / Pharmacist / Investigational Drug Storage Manager must maintain records of the product's delivery to the trial site, the inventory at the site, the use by each subject, and the return to the Sponsor or alternative disposition of unused product(s). These records will include dates, quantities, batch/serial numbers, expiry dates, and the unique code numbers assigned to the investigational product(s) and trial subjects. The Investigator / Pharmacist / Investigational Drug Storage Manager will maintain records that document adequately that the subjects were provided the doses specified by the CTP and reconcile all investigational product(s) received from the Sponsor. At the time of return to the Sponsor (or appointed CRO), the Investigator / Pharmacist / Investigational Drug Storage Manager must verify that all unused or partially used drug supplies have been returned by the clinical trial subject and that no remaining supplies are in the Investigator's possession.

### **8.2.2 Emergency code break**

Not applicable in this open label trial.

### **8.2.3 Case Report Forms (CRFs)**

All of the clinical data will be captured via electronic data capture (EDC) using the Oracle Clinical Remote Data Capture system, a web-based tool. The investigator site staff will enter and edit the data via a secure network, with secure access features (username, password and secure identification – an electronic password system). A complete electronic audit trail will be maintained. The investigator will approve the data using an electronic signature (Ref: 21 CFR Part 11), and this approval is used to confirm the accuracy of the data recorded.

Electronic CRFs (eCRFs) will be used for all patients. The investigator's data will be accessible from the investigator's site throughout the trial. Relevant medical history prior to enrolment will be documented at the baseline visit. Thereafter during the trial, narrative statements relative to the patient's progress during the trial will be maintained. The electronic

CRFs must be kept current to reflect patient status at each phase during the course of the trial. The patients must not be identified on the electronic CRF by name. Appropriate coded identification (i.e. Patient Number) must be used. The investigator must make a separate confidential record of these details (patient identification code list) to permit identification of all patients enrolled in a clinical trial in case follow-up is required. While a trial is ongoing and until the access to the database has been terminated, there will be no Documentation of Changes (DOCs). All changes will be requested from the investigator through the EDC system. If a change is necessary once the investigator has no further access to the database, a DOC will be sent to the investigator for confirmation of the change. The investigator's signature <for Japan> or seal is requested to show he/she agrees with the change that was made. The original DOC is kept by the investigator.

Copies of the electronic CRF together with all data changes made will be supplied to the investigator at the end of the trial. The investigator will be responsible for retaining all records pertaining to the trial as specified in the appropriate contract.

#### **8.2.4     Source documents**

Source documents provide evidence for the existence of the subject and substantiate the integrity of the data collected. Source documents are filed at the Investigator's site.

Data reported on the eCRFs (electronic CRFs) that are transcribed from source documents must be consistent with the source documents or the discrepancies must be explained.

The Investigator may need to request previous medical records or transfer records, depending on the study; also current medical records must be available.

The following data to be reported on the eCRF need to be included and derived from the source documents:

Subject identification (gender, date of birth)

Subject participation in the study (substance, study number, subject number)

Dates of Subject's visits

Medical history (including trial indication and concomitant diseases, if applicable)

Medication history

Adverse Events (onset date)

Serious Adverse Events (onset date)

Concomitant therapy (onset date, changes)

Originals or copies of laboratory results (in validated electronic format if available)

Originals or copies of X-rays and Ultrasound findings, ECG results, EEG results, pneumological findings, endoscopic findings and other results based on hard copies of medical equipment

Conclusion of Subject's Participation in the study

All data that has been documented in the eCRF must be documented in the source data

